18	Temperature will be recorded in a diary and recording temperature would be a requirement
19	for study participation.
20	• Duration of ANY of at least three respiratory/systemic symptom of viral illness in days
21	(Symptom 1: fever, Symptom 2: cough, Symptom 3: coryza, Symptom 4: sore throat,
22	Symptom 5: shortness of breath, Symptom 6: chills, Symptom 7: fatigue, Symptom 8: loss
23	of smell or taste, Symptom 9: myalgias, Symptom 10: arthralgias, Symptom 11: headache,
24	Symptom 12: nausea, Symptom 13: vomiting, Symptom 14: diarrhea

1	Confirmation of viral infection based on a FDA approved diagnostic test (for e	xample
2	respiratory panel PCR that also detects RSV and influenza or other respirator	y viruses, rapid
3	antigen test for SARS-CoV-2, PCR for SARS-CoV-2).	
4	• Symptomatic viral infection: proportion of participants with fever, cough, or oth	ner
5	respiratory/systemic symptoms (including but not limited to fatigue, loss of sm	ell or taste,
6	myalgias, arthralgias, shortness of breath, sore throat, headache, chills, coryz	a, nausea,
7	vomiting, diarrhea).	
8	Symptomatic moderate to severe viral infection. Based on established score s	system a viral
9	illness will be categorized as moderate or severe if the participant grades at le	east 2 different
10	symptoms as "moderate" or "severe".	
11	Symptomatic PCR confirmed SARS-CoV-2 infection	
12	Need for oxygen therapy (days)	
13	Hospitalization: Days of hospitalization attributable to viral disease: The media	an number of
14	days (or partial days) spent admitted to an acute care hospital	
15	Respiratory failure requiring ventilatory support attributable to viral disease: T	he median
16	number of days (or partial days) requiring (i) non-invasive or (ii) invasive venti	lation
17	Mortality (proportion of participants who die) attributable to viral disease and a	all-cause
18	mortality	
19		
20		
21	Outcome measures:	
22	Adverse events (day 7, 14): the proportion of participants exhibiting adver	se events of
23	any grade as defined using the established  grading scales for the severi	ty of adverse
24	event, such as the Toxicity Grading Scale for Healthy Adult and Adolesce	nt Volunteers

1	Enrolled in Preventive Vaccine Clinical Trials
2	https://www.fda.gov/media/73679/download).
3	
1	Design of Study:
5	Design of olday.
5	
6	Overview of study design
7	Open label clinical trial (intervention with a diet supplement) to evaluate the safety and efficacy

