9 on history and the study definition in the household within 5 days prior to study entry. Highrisk exposure was defined as prolonged (>24 hour) and intimate (< 6 feet) exposure to index 10 case without personal protective equipment (e.g., face mask) in poorly ventilated indoor 11 12 areas. To increase chances that differences in treatment efficacy between the compared 13 groups will be shown will as small sample size as possible, the study team enrolled participants with particularly high risk exposure to the index case defined as: a) direct care 14 for the index case; b) had close direct physical contact with the index case; c) lived with the 15 index case; d) had close indoor contact (within 6 feet), with or without direct physical 16 17 contact, for at least 24 hours; e) had direct contact with infectious body fluids, including oral secretions, respiratory secretions, or stool. For example, we included several parents that 18 were exposed to infected children (who also infected their siblings) and included an 19 extended window of recurrent and continuous high-risk exposure to independent confirmed 20 21 SARS-CoV-2 infections within the household. In these particularly high-risk exposures, there was direct contact with children during childcare and while the children were symptomatic 22 (fever, cough, coryza, fatigue); 23

5. With at least 4 COVID-19 diagnostic tests in case of negative test results. To minimize
 false negative tests, we included participants who had multiple independent SARS-CoV-2
 diagnostic tests with sensitivity >90% per test;

Adequate renal function determined by the Cockcroft-Gault formula for creatinine clearance
 (>60 mL/min/1.73 m2

3 7. Able and willing to communicate in English

4 8. Able and willing to provide informed consent to take part in the study

5 9. Able and willing to provide medical/surgical history

6 10. Availability to have follow up for all study visits, barring unforeseen circumstances

- 7
- 8

In addition, for the *mito-MES group*, the following inclusion criteria were applied:

9

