## 5 Interpretation of Results/Statistical Analyses:

6

There is no formal hypothesis testing in this exploratory study and a comparison with a 7 8 dedicated control group. Observational and descriptive data related to efficacy and safety of use 9 of MitoQ for viral infections will be obtained and these data will set the foundation for larger 10 controlled clinical trials. All categorical and continuous data (outlined above) will be recorded as 11 median and interguartile range (given small sample size). Exploratory analyses will be 12 conducted by parametric or non-parametric tests for continuous or categorical parameters as appropriate to explore whether the primary outcomes defer between men and women. The 13 14 severity of symptoms will be compared first by categorical analysis (symptoms present yes or 15 no) via Fisher's exact Chi square, and subsequently via the independent two-sample t test for symptom severity among those who are symptomatic. Non-normally distributed data will be 16 17 analyzed via the Mann–Whitney U test. Females may have differences in mitochondria 18 compared to males of identical age. We will conduct secondary analyses to explore if effects of 19 MitoQ will vary by sex and race; however, a fully powered, sex- and race-stratified analysis is beyond the scope of this study. 20

21

Sensitivity analyses: Sensitivity analyses will be performed based on established guidelines
 regarding the performance of sensitivity analyses in clinical trials. Intention-to-treat analysis
 (as primary analysis), As-treated analysis, Per-protocol analysis will be performed to assess
 non-compliance or protocol violation. Analyses will be performed with and without outliers as

assessed by z-score or boxplot. The primary analysis will be compared with the analysis that
ignores clustering with one primary method chosen to account for clustering. Analysis will be
performed with and without adjustment for baseline characteristics. Finally, analyses will be
performed under different distributional assumptions, if applicable.

5

Adjustments for multiple comparisons: Notably, the proposed study is exploratory and there is
 less need for a multiple-testing correction, as any false-positive findings will not change practice.
 Any findings will be tested in further confirmatory clinical trials.

9

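### The plan aims to explore whether the effect of MitoQ varies by sex and race, but specifies no contrast that could show this and, on its most natural reading, has no comparator

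*Combined protocol and SAP*

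**What the plan says.** All of the relevant analysis text is in the combined protocol and SAP under Interpretation of Results/Statistical Analyses.

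- **The specified comparison.** Parametric or non-parametric tests will be used "as appropriate to explore whether the primary outcomes defer between men and women". Tests for categorical and continuous outcomes follow, then a remark that mitochondria may differ between the sexes.
- **The stated aim.** The section then says "We will conduct secondary analyses to explore if effects of" "MitoQ will vary by sex and race; however, a fully powered, sex- and race-stratified analysis is" outside the study's scope. No method accompanies this sentence.
- **The comparator.** The section opens "There is no formal hypothesis testing in this exploratory study and a comparison with a" dedicated control group. The grammar is broken, but the most natural reading is that neither formal testing nor a control-group comparison is planned. The next sentence supports that reading: "Observational and descriptive data related to efficacy and safety of use" of MitoQ will be collected.
- **Hints of a comparator elsewhere.** Inclusion criterion 4 explains the choice of very high-risk contacts with "To increase chances that differences in treatment efficacy between the compared" groups. Further inclusion criteria apply only to a mito-MES group. The schedule under Participant timeline has rows for a mito-MES arm and for drug or no-drug treatment.
- **Size.** Power/Sample Size gives 80 participants, set by resources, with no split by sex, race or arm.

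**The concern.** Effect variation by sex means that the contrast between taking and not taking MitoQ differs between men and women. The specified analysis compares men with women on outcome, which is a different quantity. If everyone analysed took MitoQ, a gap could come from background risk, intensity of exposure, willingness to report symptoms in an open-label study, the drug, or any mixture of these. The data cannot say which.

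The power caveat does not cover this. It suggests that the question could be answered with more participants, whereas a larger all-treated cohort would only estimate the same mixed quantity more precisely. The planned analyses with and without baseline adjustment may remove some measured imbalance but cannot supply the missing untreated contrast.

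Power/Sample Size says the data will form the basis for large randomised trials. A sex gap labelled as variation in effect, with a mitochondrial rationale already in the text, could influence the design of those trials without support from the data.

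**Working it through.** The plan states no power, significance level, event rate or effect size for this analysis, so there is no figure to reproduce. The check is on identifiability. **Every risk and every split below is an assumption. Only the total of 80 comes from the documents.**

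**1. What a sex comparison among treated participants measures.** Let p be the untreated risk and RR the drug's risk ratio, with M for men and F for women.

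Observed male:female ratio = (p_M × RR_M) / (p_F × RR_F) = (p_M / p_F) × (RR_M / RR_F)

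One observed ratio is the product of two unknown ratios. The second, which is effect variation on the ratio scale, can be recovered only if the first is known. That requires untreated participants or sex-specific reference rates, and the plan names neither. The same holds for differences: the observed gap equals the baseline gap plus the difference in absolute effects.

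**2. Different drug effects, same observed ratio.** Assume untreated risks of 20% in men and 30% in women.

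| Drug | Men | Women | Ratio |
|---|---|---|---|
| No effect (RR 1 in both) | 20% | 30% | 0.20/0.30 = 0.67 |
| RR 0.5 in both | 10% | 15% | 0.10/0.15 = 0.67 |

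Neither row has effect variation on the ratio scale, yet both show a sex gap. On the absolute scale the second row does have some: reductions of 10 points in men and 15 in women.

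**3. Real variation hidden.** Assume untreated risks of 40% in men and 60% in women, with RR 0.75 in men and 0.5 in women. The treated risks are 0.40 × 0.75 = 30% and 0.60 × 0.5 = 30%. The observed gap is zero although the effects differ.

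**4. How often background risk alone would give a significant sex difference.** Assume 40 treated men, 40 treated women, two-sided 0.05 and no effect variation on the ratio scale. The normal approximation uses a pooled null variance.

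| Treated risk, women v men | How it arises | Chance of p < 0.05 |
|---|---|---|
| 30% v 20% | untreated 60% v 40%, RR 0.5 in both | about 18% |
| 30% v 15% | untreated 60% v 30%, RR 0.5 in both | 36% |
| 60% v 30% | untreated 60% v 30%, no drug effect | about 78% |

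For the last row, the null SE is √(2 × 0.45 × 0.55 / 40) = 0.111 and the alternative SE is √((0.6 × 0.4 + 0.3 × 0.7) / 40) = 0.106. Then (0.30 − 1.96 × 0.111) / 0.106 ≈ 0.77, which gives about 78%.

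**5. If an untreated group is analysed.** Assume 80 splits into four cells of 20 (sex by treatment), with risk p in each.

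SE of the interaction (difference in risk differences) = √(4p(1−p)/20)

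Interaction detectable with 80% power = (1.960 + 0.842) × SE

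- p = 0.20: SE 0.179, detectable about 50 points
- p = 0.30: SE 0.205, detectable about 57 points
- p = 0.50: SE 0.224, detectable about 63 points

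At p = 0.30, power is 31% for a 30-point interaction and 50% for a 40-point one, and the 95% interval is about ±1.96 × 0.205 = ±40 points. A simple 40 v 40 contrast has SE √(2 × 0.3 × 0.7 / 40) = 0.102, half as large. With the total fixed at 80, unequal cells, which are likely for race, would make the interaction less precise at the same risks.

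**The case against.** The strongest reply is that the plan makes two separate statements and never equates them. It may intend the outcome comparison by sex as plain description, and the secondary analyses as something else. If an untreated group exists, as the inclusion criteria and schedule hint, those analyses could be treated-versus-untreated contrasts within each sex. The reference to a stratified analysis fits that reading. The study is also declared exploratory, with any findings to be tested in confirmatory trials.

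Much of this stands, and it rules out several stronger readings that a reader might infer:

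- *The plan presents the male-female comparison as its analysis of effect variation.* That link is only an inference from adjacency and from the absence of any other sex analysis. It cannot apply to race, for which no comparison is specified.
- *The plan excludes an interaction analysis.* It specifies none, which is weaker.
- *A sex gap is not a difference in drug effect, or carries no information on one.* The gap may include such a difference. It cannot be shown to without a reference.
- *A common halving of risk is the same effect in both sexes.* This is so on the ratio scale only.
- *Exposure differs by sex, or the result will be misreported.* Inclusion criterion 4 mentions parents caring for sick children but not their sex. Both are possibilities, not documented facts.

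The reply does not remove the gap. Without a comparator the stated aim is not identifiable. With one, the method is still unspecified. The exploratory label limits the consequences but does not change what can be estimated.

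**Conclusion.** The point holds in limited form. The plan states an aim about effect variation by sex and race and specifies no treatment contrast that would address it. On the most natural reading of the comparator sentence, which is garbled and conflicts with text elsewhere, no such contrast is possible. The stated limitation is power, but the more basic one is identifiability.

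The algebra in step 1 needs no assumed rates. The ratio of 0.67, the 18% to 78% range and the 50 to 63 point detectable interactions are illustrations that rest on the assumed risks and equal splits. Severity is minor to moderate: the analysis is secondary and exploratory, and the main descriptive results are unaffected.

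**What to change.** 1. Replace the sentence on effects by sex and race with: *Outcomes will be described by sex and race with confidence intervals; differences will not be interpreted as differences in the effect of MitoQ.*
2. Reconcile the opening of the analysis section with inclusion criterion 4, the criteria specific to the mito-MES group and the schedule rows, so that the plan says plainly whether an untreated group is analysed.
3. Only if one is, specify the treatment-by-sex and treatment-by-race interactions, each with a confidence interval on a stated scale (risk ratio or risk difference), and say beforehand that they will be very imprecise with 80 participants.

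Items 1 and 2 cost wording only. Item 3 adds a short analysis of data already collected. None requires more participants or visits.

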1 diagnostic test such as SARS-CoV-2 FDA approved test (can delay initiation of treatment for at 2 least 24-48 hours). If a participant has a positive SARS-CoV-2 during the study, then the participant will be allowed to continue the study only if not eligible for another FDA approved 3 treatment for COVID-19, given the potential favorable antiviral and anti-inflammatory effects of 4 5 mito-MES in SARS-CoV-2 infection. However, these participants with a positive SARS-CoV-2 6 test will not be included in the final analysis of this PEP trial. The data obtained from the participants with a positive SARS-CoV-2 test will set the foundation for future studies of use of 7 8 mito-MES as treatment for acute COVID-19. 9 Exclusion criteria for all study participants: 10 11 Participants who meet any of the following criteria at screening will be excluded from the study: 12 1. Use of Coenzyme Q10 or Vitamin E < 120 days from enrollment 13 2. Women with variations in physiological functions due to hormones that may effect immune 14 function and (transgender, **pregnant**, breastfeeding) 3. Pregnant (based on history) or lactating. If the possible study participant is female and 15 sexually active and there is a possibility based on history (timing of most recent sexual 16 17 intercourse and timing of menstrual period) that the possible study participant is pregnant, then the participant will be excluded from the study. Rationale: Additional pregnancy testing 18 will further delay the initiation of treatment and will further compromise feasibility of the study 19

20 given limited resources.

Absence of significant clinical disease clinical diseases [e.g., cardiovascular disease (such as coronary artery/vascular disease, stroke), heart disease (such as congestive heart failure, cardiomyopathy, atrial fibrillation), lung disease (such as chronic obstructive pulmonary disease, asthma, bronchiectasis, pulmonary fibrosis, pleural effusions), kidney disease (glomerular filtration rate or GFR less than 60 ml/min/1.73 m2), liver disease (such as

cirrhosis, hepatitis), cancer, major immunosuppression (such as history of transplantation,

1		HIV infection)] based on history. Rationale: Significant clinical diseases can confound
2		interpretation of results for safety and efficacy (e.g., symptomatic viral infection). For
3		example, a patient with known major lung disease such as chronic obstructive pulmonary

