14	Intervention in adults: Exposure of a potential study participant to a viral infection (whether it
15	was confirmed by an FDA approved diagnostic test or not) in a close contact within the
16	household of the study participant and which may cause severe disease in humans (such as
17	SARS-CoV-2 infection or influenza). Intervention would be 20 mg (4 drug capsules) PO daily
18	initiated within 5 days post exposure and taken daily for up to 14 days.
19	
20	Dose Justification
20	
21	
22	Dose justification
23	In a randomized controlled clinical trial of patients with Hepatitis C (ClinicalTrials.gov Identifier:
24	NCT00433108) mito-MES 40 mg orally daily had anti-inflammatory activity (reduced hepatitis) in

1 an epithelial tissue (liver). Mito-MES is commercially available as a dietary supplement in dose 2 of 10 mg orally daily. The dose of mito-MES that is typically used in clinical trials in humans is 20 mg orally daily. It is likely that a higher dose (40 mg daily) is more effective against SARS-3 CoV-2 infection (better antiviral and anti-inflammatory effects) than the lower dose (20 mg daily). 4 5 Thus, in a proof-of-concept initial study we will test the tolerability and efficacy of the 20 mg 6 dose of mito-MES that can be well tolerated in humans over a period of 14 days (20 mg PO daily). The 80 mg oral dose of mito-MES daily is also well tolerated based on clinical trials in 7 humans but gave higher incidence of gastrointestinal side effects. 8 9 10 Justification of 20 mg dose for penetration in respiratory mucosa. 11

Oral MitoQ can achieve adequate levels in the respiratory mucosa that can inhibit establishment
 of early SARS-CoV-2 infection

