#### 17 *Retention:*

18

Site investigators are trained about the importance of retention and steps to prevent missing data. To increase subject retention, all subject questions/concerns will be addressed in detail during the consent process. The consent forms will include a statement educating patients about the continued scientific importance of their data even if they discontinue study treatment early. The protocols and informed consent forms will clearly differentiate treatment discontinuation from study withdrawal. There will be constant communication will occur between research staff and participants through phone-call and email reminders prior to all upcoming

1 visits. Several approaches will be implemented to retain patients who fail to actively maintain 2 contact with the investigator (e.g., telephone calls, texts, and emails to the patient and close contacts; vital records search). The study will be conducted through the phone which is easily 3 accessible to participants. All patients who maintain consent will be followed for additional 4 5 outcome information and will remain in the study through the end of the study period for all 6 important safety and efficacy assessments. The only reasons for study withdrawal will be withdrawal of consent and loss to follow-up. Sponsors and investigators will encourage patients 7 8 who discontinue therapy to remain in the study and to continue follow-up for key outcomes. 9 Through these strategies, the investigators have recruited participants with specific interest in participating in research, leading to high rates of retention of study subjects, with high level of 10 11 retention of volunteers in clinical studies even without the need for financial incentives.

12

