## 6 Power/Sample Size:

7

8 The study is purely exploratory and is not powered to do a formal hypothesis testing. The data 9 from this study will set the basis for large randomized controlled clinical trials to test the safety of 10 mito-MES in the setting of treatment of viral illnesses. In addition, preliminary data will be 11 obtained on the efficacy of Mito-MES to reduce severity of viral illness. More specifically, all the proposed primary endpoints of efficacy are based on objective quantifiable criteria (fever based 12 on thermometer, duration of symptoms based on number of days, severity of viral illness based 13 14 on quantitative summary score that considers at least two independent symptoms of viral illness based on a clinically relevant definition of viral illness made by a physician). The "effect size" of 15 16 the intervention Mito-MES on these quantifiable outcomes of viral illness in humans will be 17 determined. The safety of Mito-MES in the setting of viral illness will be recorded. This is essential information for the design of larger RCT studies. 18

19

20 Based on resources, we enrolled 80 study participants.

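### The as-treated and per-protocol sets are undefined, and their ordinary definitions would count adherence after symptom onset, which can be a consequence of the outcome

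*Combined protocol and SAP*

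**What the plan says.** The Sensitivity analyses paragraph under Interpretation of Results/Statistical Analyses makes intention-to-treat primary and adds "As-treated analysis, Per-protocol analysis will be performed to assess" non-compliance or protocol violation. It gives no adherence threshold, no time window and no rule for an early stop.

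Other sections bear on what the two sets would mean:

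- **Duration.** Duration of treatment justification gives 14 days. Treatments (Intervention in adults) says "initiated within 5 days post exposure and taken daily for up to 14 days", which leaves open whether an early stop is non-adherence.
- **Diaries.** Participant timeline and Sessions by study participant have adherence, symptoms and temperature recorded daily on days 1 to 14.
- **Outcome.** Main Parameters of Efficacy counts any symptom within 14 days after exposure, largely the same days.
- **Positive test.** The paragraph just before the exclusion criteria says that after a positive SARS-CoV-2 test the "participant will be allowed to continue the study only if not eligible for another FDA approved" treatment. It also leaves participants with a positive test out of the final analysis.
- **Follow-up.** Retention encourages patients "who discontinue therapy to remain in the study and to continue follow-up for key outcomes".
- **Comparator.** The analysis section says "There is no formal hypothesis testing in this exploratory study and a comparison with a" dedicated control group, which appears to deny one. The eligibility section has extra criteria for a mito-MES group and the schedule has a drug/no drug row; both imply an untreated group.

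**The concern.** A per-protocol set normally keeps people who took enough of the planned course, and an as-treated analysis groups people by what they took. With a 14-day course and a 14-day diary, both would ordinarily use days after symptom onset. A participant who falls ill on day 4 and stops on day 5 would then be a non-adherer because of the outcome. Per-protocol removes that person. As-treated counts that person's illness as untreated.

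The documents make such stopping plausible without stating it. Nausea, vomiting and diarrhea are outcome symptoms, and Dose Justification reports some attrition from gastrointestinal discomfort (below 5% at 40 mg/day) in previous trials. Missing data foresees participants too ill to record for themselves; verbal responses are planned, but any diary day still missed could be read as a missed dose.

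At stake is the effect size that Power/Sample Size says will inform larger trials. Two supportive analyses with the same selection could appear to confirm each other.

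**Working it through.** The plan has no calculation to reproduce: its only figure is "Based on resources, we enrolled 80 study participants". Attack rates, stopping rates and group split below are all assumptions.

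**1. All 80 on an inactive drug, 24 ill (30%), 56 well.** Per-protocol rate = ill continuers / all continuers.

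| Ill who stop | Well who stop | Continuers (per-protocol) | Stoppers |
|---|---|---|---|
| 12 of 24 | 0 of 56 | 12/68 = 18% | 12/12 = 100% |
| 6 of 24 | 0 of 56 | 18/74 = 24% | 6/6 = 100% |
| 12 of 24 | 8 of 56 | 12/60 = 20% | 12/20 = 60% |
| 12 of 24 | 28 of 56 (equal) | 12/40 = 30% | 12/40 = 30% |
| 0 of 24 | 8 of 56 (reverse) | 24/72 = 33% | 0/8 = 0% |

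The true rate is 30% in every row. Without a comparator, per-protocol merely shifts a descriptive rate. The misleading contrast would be continuers against stoppers.

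**2. With an untreated group (assumed 40:40, inactive drug).** Let p be the attack rate, s1 the stopping probability in the ill and s0 in the well.

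- Per-protocol risk on drug = p(1 − s1) / [p(1 − s1) + (1 − p)(1 − s0)], compared with p.
- As-treated untreated risk = [40p + 40·p·s1] / [40 + 40(p·s1 + (1 − p)s0)].

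Example with p = 0.4, s1 = 0.30, s0 = 0.05: per-protocol risk = 0.28/(0.28 + 0.57) = 0.329, risk ratio 0.329/0.4 = 0.82. As-treated untreated risk = (16 + 4.8)/(40 + 6) = 0.452, risk ratio 0.329/0.452 = 0.73.

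Over p = 0.2 to 0.6 (true risk ratio 1.00):

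| s1 | s0 | Per-protocol risk ratio | As-treated risk ratio |
|---|---|---|---|
| 5% | 5% | 1.00 | 1.00 |
| 10% | 5% | 0.96–0.98 | 0.92–0.96 |
| 30% | 5% | 0.78–0.87 | 0.66–0.81 |
| 50% | 5% | 0.58–0.74 | 0.44–0.65 |
| 5% | 30% | 1.12–1.27 | 1.22–1.51 |

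As-treated is further from 1 because stoppers also change the comparison group.

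**3. Check of the remedy.** Take the third row of step 1 and assume that all 12 ill stoppers stopped after onset. Counting the whole course gives 12/60 = 20%. Counting only days before onset keeps all 24 ill and removes the 8 well stoppers: 24/72 = 33%. The error goes from 10 points too low to about 3 points too high. It is smaller, but not zero.

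**4. Positive tests.** If a share q of the ill test positive and are left out, the remaining risk is p(1 − q)/[p(1 − q) + 1 − p]. With p = 0.4 and q = 0.5 this is 0.2/0.8 = 0.25. If only the drug group is affected, the risk ratio is 0.25/0.4 = 0.63 for an inactive drug, with no adherence rule involved.

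**The case against.** A reader might infer that the plan classifies people by adherence through day 14, that illness makes people stop the capsules, and that both analyses must therefore manufacture a benefit. The documents do not support this. No classification rule is written, dosing is for up to 14 days, no stopping rate is given, and step 2 shows no bias at equal stopping and apparent harm if well people stop more.

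A reader might also take the positive-test rule as the mechanism. That route is largely closed: read literally, anyone testing positive leaves the final analysis whatever their adherence, and so cannot become an as-treated stopper. Nor does the plan say that it will compare continuers with stoppers.

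The consequences are also limited. Intention-to-treat is primary, stoppers are followed, and Power/Sample Size says: "The study is purely exploratory and is not powered to do a formal hypothesis testing".

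All of this stands as a limit on the claim. What remains is that two named analyses have no definition, their ordinary definitions can select on the outcome, and a disagreement with intention-to-treat could not be attributed to non-compliance.

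**Conclusion.** The point holds as a gap in definition with a conditional bias. Under the ordinary definitions, an excess of stopping among the ill makes an inactive drug look better. With 5% stopping among the well and an assumed 40:40 split, the effect is negligible to small at 10% stopping among the ill and substantial at 50%. These rates are not in the documents, so neither size nor direction can be predicted. The as-treated contrast also depends on whether an untreated group exists, on which the documents conflict. The primary analysis is not affected by this point. It is affected by the exclusion of SARS-CoV-2 positives, which selects on the outcome and contradicts an intention-to-treat primary analysis.

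**What to change.** Add to the Sensitivity analyses paragraph:

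1. Classify adherence only on days before the first symptom or first positive test (through the end of the course if neither occurs), as a proportion of days at risk, with a stated threshold. Stopping after onset then never removes or reclassifies anyone.
2. Make no comparison of continuers with stoppers.
3. Keep participants who fall ill before their first dose in the intention-to-treat set, and report how many there are. Requiring a dose before onset would drop ill people while keeping well ones.
4. Keep intention-to-treat primary and report the other two analyses as supportive only. State their remaining weakness: well participants have a longer window in which to become non-adherent, so some bias in the other direction can persist (step 3).
5. Reconcile the exclusion of SARS-CoV-2 positives from the final analysis with the intention-to-treat statement. This concerns who is analysed, not how anyone is managed.

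The cost is wording and a small amount of programming, since the dated daily diaries already supply the data. Because enrolment is described as done, fix the definitions before outcomes are examined, or state that they were set afterwards.
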